**Table 3: PFS2 Event and Censoring Method**

Situation	Date of Progression or Censoring	Outcome
No postbaseline disease assessment	Randomization	Censored
Alive and no disease progression on study treatment	Date of last disease assessment prior to start of 1st line on next therapy	Censored
Disease progression on study treatment and progress on the 1 st line of next therapy or any death	Minimum of earliest date that indicates progression on the 1 st line of next therapy and date of death	PFS2 event
Other	Minimum of start date of 2 nd line of next therapy minus 1 and last date of follow-up	Censored

#### 5.4.2.2. Analysis Methods

PFS2 based on investigator assessment on ITT analysis set will be analyzed using similar statistical methods as described in Section 5.3.1.2 for PFS analysis.

### 5.5. Subgroup Analysis for Efficacy Endpoints

For assessment of internal consistency and investigation of homogeneity of the treatment effect across subgroups, a subgroup analysis of the primary efficacy endpoint of ORR based on pre-specified subgroups defined in Section 2.10 will be conducted.

A forest plot of subgroup analysis on ORR will be generated.

Additional exploratory subgroup analyses may be performed for selected efficacy and/or safety endpoints.

## **6. SAFETY**

Analysis of safety data will be provided on the safety analysis set. All subjects will be analyzed according to the actual treatment they received.

The safety assessments to be evaluated include AEs, deaths, clinical laboratory tests (hematology, chemistry), vital signs, electrocardiogram (ECG) and ECOG performance scores.

### **6.1. Adverse Events**

AEs will be recorded in standard medical terminology and graded according to the National Cancer Institute Common Terminology Criteria for Adverse Events (NCI-CTCAE), Version 4.03. For AE reporting, the verbatim term used in the CRF by investigators to identify adverse events will be coded using the latest version of Medical Dictionary for Regulatory Activities (MedDRA) coding dictionary.

The relationships to study medication will be recorded as not related, doubtful, possible, probable, or very likely on eCRF for all the AEs. Adverse events will be categorized and summarized according to their highest relationship to study medication. An adverse event is considered as related to study medication if the relationship is recorded as possible, probable or very likely.

Treatment-emergent adverse events (TEAEs) are defined as any AE with onset date and time on or after that of the first dose through 30 days after the last study drug administration, or the day prior to start of subsequent therapy, whichever is earlier; or the follow-up AE (linked to an existing TEAE) with onset date and time beyond 30 days after the last study agent administration but prior to the start of subsequent therapy; or any AE that is considered related to (very likely, probably, or possibly related) study medication regardless of the start date of the event; or any AE that is present at baseline but worsens in toxicity grade or is subsequently considered drug-related by the investigator. AEs with missing or partial onset date and time will be considered as treatment-emergent unless the onset date and time of an AE can be determined as earlier than that of the first dose, or later than 30 days after last study drug administration.

Unless otherwise specified, at each level (e.g., system organ class and/or preferred term) of subject summarization in reporting the incidence of the AE, a subject is counted once if one or more events were recorded. For summarizing new onset events, all event records of the same preferred term from the same subject are to be linked by the onset date and the end date. If an event is followed by another event of the same preferred term with an onset date (or date/time) the same as or 1 day (or 1 minute if applicable) after the end date (or date/time) of the previous record and any features of the adverse event (i.e.: toxicity grades/seriousness/action taken) are different between these two records, these 2 records should be linked together and considered as

1 event. A Grade 5 event will be linked to previous event of the same preferred term if the onset date of Grade 5 record is the same or one day after the end date of previous record.

### **6.1.1. Overview of TEAEs**

An overview of TEAEs reported through the study will be provided for each treatment group. Overall summary of TEAE will include the subjects with TEAEs, serious TEAEs, TEAEs of maximum toxicity grade of 1 to 5, and TEAEs leading to treatment discontinuation.

A similar overview of TEAEs will be presented by treatment cycle.

### **6.1.2. All TEAEs**

The following summaries will be provided for all TEAEs:

- TEAEs by system organ class (SOC) and preferred term (PT)
- Most common (e.g.,  $\geq 10\%$ ) TEAEs by SOC and PT
- TEAEs by SOC, PT, and maximum toxicity grade

### **6.1.3. Toxicity Grade 3 or 4 TEAEs**

The following grade 3 or 4 TEAEs will be summarized:

- Grade 3 or 4 TEAEs by SOC and PT
- Most commonly reported (e.g.,  $\geq 5\%$ ) grade 3 or 4 TEAE by SOC and PT

A similar summary of grade 3 or 4 TEAEs will be presented by SOC, PT and by treatment cycle.

In addition, a listing of grade 3 or 4 TEAEs will also be provided.

### **6.1.4. Treatment-related TEAEs**

The following TEAEs will be summarized by relationship to study drug:

- TEAEs by SOC, PT, and relationship
- Grade 3 or 4 TEAEs by SOC, PT and relationship

### **6.1.5. Serious TEAEs**

The incidence of serious TEAEs will be summarized as below:

- Serious TEAEs by SOC and PT
- Serious TEAEs by SOC, PT and relationship to study drug
- Most commonly reported (e.g.,  $\geq 2\%$ ) serious TEAEs by SOC and PT

A similar summary of serious TEAEs will be presented by SOC, PT and treatment cycle.

In addition, a listing of serious TEAEs will be provided.

### **6.1.6. TEAEs Leading to Treatment Discontinuation**

The TEAEs leading to permanent treatment discontinuation will be summarized by SOC, PT and grade 3/4 for those subjects indicated as having discontinued treatment with study drug due to an adverse event on the eCRF “End of Treatment” page.

A listing for subjects who discontinued treatment with study drug due to AE will be provided.

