6.4.2. Infusion-related Reactions

Subjects should be observed carefully during study drug administrations. Trained study staff at the clinic should be prepared to intervene in case of any IRRs, and resources necessary for resuscitation (eg, agents such as epinephrine and aerosolized bronchodilator, also medical equipment such as oxygen tanks, tracheostomy equipment, and a defibrillator) must be available at the bedside.

If an IRR develops, then the infusion or injection should be temporarily interrupted or slowed down. Subjects who experience adverse events during the infusion must be treated for their symptoms. Subjects should be treated with acetaminophen, antihistamine, or corticosteroids as needed. Intravenous saline may be indicated. For bronchospasm, urticaria, or dyspnea, subjects may require antihistamines, oxygen, corticosteroids, or bronchodilators. For hypotension, subjects may require vasopressors. In the event of a life-threatening IRR (which may include pulmonary or cardiac events) or anaphylactic reaction, daratumumab should be discontinued and no additional daratumumab should be administered to the subject. Aggressive symptomatic treatment should be applied. In case of interruption of the administration of the study drug due to an adverse event related to the study drug, the investigator/study coordinator should review the information of the dispensed study drug on the IPPI and ensure the correct drug product is being used before restarting the administration.

If an infusion/injection is paused or the infusion rate is decreased, then a longer-than-anticipated infusion/injection time may occur. Overnight stays at the hospital because of slow infusion/injection times should not be reported as serious adverse events. However, if the underlying cause of the delayed infusion/injection time is an adverse event or serious adverse event, then that should be reported as such.

Infusion-Related Reactions of Grade 1 or Grade 2

If the investigator assesses a Grade 1-2 IRR adverse event to be related to administration of study drug, then the Dara-IV infusion or Dara-SC injection should be paused. Once IRR symptoms resolve and the subject's condition is stable, the Dara-IV infusion or Dara-SC injection may be restarted at the investigator's discretion. Upon restart of Dara-IV infusion, the infusion rate should be half of that employed before the interruption. If the subject does not experience any

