10. SUBJECT DISCONTINUATION OF STUDY TREATMENT/ WITHDRAWAL FROM THE STUDY

10.1. Discontinuation of Study Treatment

Discontinuation of Study Treatment

If a subject's study treatment must be discontinued, this will not result in automatic withdrawal of the subject from the study. The End-of-Treatment Visits and Follow-up visit assessments should continue as specified in the Time and Events Schedule.

A subject's study treatment must be discontinued if:

- The investigator believes that for safety or tolerability reasons (eg, adverse event) it is in the best interest of the subject to discontinue study treatment.
- The subject becomes pregnant unless the subject (or the subject's legally acceptable representative), investigator, and sponsor agree the benefits outweigh the risks to the fetus and continuation of study treatment is in the best interests of the subject
- The subject (or the subject's legally acceptable representative) withdraws consent for administration of study drug
- The subject experiences unacceptable toxicity, including IRRs described in Section 6.4, Management of Injection-site and Infusion-related Reactions
- The subject's dose is held for more than 28 days, or if 3 consecutive planned doses of daratumumab are missed for reasons other than toxicity unless, upon consultation with the sponsor and the review of safety and efficacy, continuation is agreed upon
- The subject experiences disease progression (please see below); relapse from CR is not considered as disease progression
- The subject experiences a second primary malignancy that cannot be treated by surgery alone (however, a subject who develops a malignancy that can be cured surgically may continue to receive the assigned study treatment and should continue to be followed for subsequent progression of multiple myeloma)

The primary reason for discontinuation of study treatment will be recorded in the eCRF.

Study treatment will continue until confirmation of PD. Before subjects are discontinued from study treatment because of suspected PD:

1. The investigator (or designee) will provide documentation of disease progression (for example, by completing a disease progression form or by contacting the IWRS) as soon as possible and within 48 hours of confirmation of disease progression.

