#### 4.1. Subject Disposition

The number of subjects who are randomized, treated, ongoing, and discontinued treatment with reasons of discontinuation reported on eCRF will be summarized. The number of subjects who discontinued from study with the reported reasons will also be presented. The number of subjects who discontinued treatment by cycle with the reported reasons will also be provided.

Subject enrollment will also be summarized by country and site for intent-to-treat analysis set.

A listing of subjects who discontinued treatment with study drug including reasons for discontinuation will be provided. A similar listing will be provided for subjects who discontinued study.

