### **6.1.7. TEAEs Leading to Treatment Modifications**

Incidence of TEAEs leading to treatment modifications (i.e., cycle delay, dose delays, or dose skip) will be summarized by SOC, PT and grade 3/4 for each treatment group.

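### SAP 6.1.6 can omit adverse events that ended treatment, and SAP 6.1.7 has no place for those that interrupted or stopped an administration

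*SAP*

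**What the plan says.** **Discontinuation.** SAP 6.1.6 restricts its table to events "for those subjects indicated as having discontinued treatment with study drug due to an adverse event on the eCRF" End of Treatment page, and its listing covers the same group. Protocol 10.1 states: "The primary reason for discontinuation of study treatment will be recorded in the eCRF". SAP 4.1 describes the disposition summary as subjects who "discontinued treatment with reasons of discontinuation reported on eCRF". SAP 6.1, when explaining how consecutive records of one event are linked, names the features of an event record as "toxicity grades/seriousness/action taken".

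**Modification.** SAP 6.1.7 reads: "Incidence of TEAEs leading to treatment modifications (i.e., cycle delay, dose delays, or dose skip) will be summarized by SOC, PT and grade 3/4". Protocol 6.4.2 says that if the investigator judges a Grade 1-2 infusion-related reaction (IRR) related to the drug, "then the Dara-IV infusion or Dara-SC injection should be paused". At Grade 3 the administration is to be stopped and may later be restarted. The section also mentions slowing the administration. SAP 4.7 summarizes what was done during infusion or injection, with the eCRF reasons, under extent of exposure.

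**The concern.** A table of adverse events leading to discontinuation is normally read as a count of events that ended treatment. Here it counts events in subjects whose recorded reason was an adverse event, and the restriction can only remove events. SAP 6.1.1 carries a line for TEAEs leading to discontinuation in the overview, and SAP 6.3.7 repeats that overview by subgroup. If 6.1.6 governs that line, any shortfall carries over.

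The list in 6.1.7 is introduced by an i.e. and is therefore closed. A reader who wants to know which events broke off an infusion or injection will not find them there. Safety by route is a secondary objective, and fewer IRRs are part of the stated case for SC dosing (protocol 1.4), so both tables will be read as comparisons between the arms.

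**Working it through.** The plan gives no figure to reproduce, so the check is mainly of definitions.

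**1. Discontinuation.**
- Counting rule (SAP 6.1.6): the End of Treatment reason must be an adverse event.
- Data collected (protocol 10.1): the primary reason.
- Grounds for stopping listed in protocol 10.1 include safety or tolerability, with adverse event as the example. Listed separately are unacceptable toxicity, a hold of more than 28 days, withdrawal of consent for the drug, progression, and this one: "The subject experiences a second primary malignancy that cannot be treated by surgery alone".
- Event-level information: SAP 6.1 treats action taken as part of the event record, but 6.1.6 does not use it.

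Taken together, a TEAE whose own record shows the drug was withdrawn is left out if the site entered, for example, withdrawal of consent as the primary reason.

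**2. Modification.**
- In the 6.1.7 list: cycle delay, dose delay, dose skip.
- In protocol 6.4.2 but not in the list: administration paused, slowed or stopped.
- Covered elsewhere: SAP 4.7 gives the frequency of actions during administration with reasons. SAP 6.3.1.2 gives IRR incidence by SOC, PT and grade 3/4, but not the action taken.

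The missing piece is one table linking the event, by SOC and PT, to the interruption or stop.

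**3. Illustration of size.** The documents do not say how often a reason is filed elsewhere or how often an IRR leads to a pause. The shares below are assumptions, and the results are not estimates.
- Discontinuation: protocol 1.2.1.1 reports 6 of 156 Dara-IV subjects stopping for a TEAE, and 6/156 = 3.8%. With 240 per arm that is 240 × 6/156 = 9.2 subjects. If a share s is filed under another reason, the table shows 3.8% × (1 − s). For s from 0 to 0.5 this runs from 3.8% to 1.9%, or from 9.2 to 4.6 subjects.
- Interruption: protocol 1.3.2 gives IRR rates of about 50% for Dara-IV, and 24% (1800 mg) and 13% (1200 mg) for Dara-MD, the mix-and-deliver SC presentation. If a share f of subjects with an IRR had a pause or stop, the same in both arms, the between-arm difference not shown in 6.1.7 is (50% − SC rate) × f. At 24% it runs from 26 × 0.25 = 6.5 to 26 × 1 = 26 percentage points. At 13% it runs from 37 × 0.25 = 9.2 (rounded) to 37 points.

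The direction, more on IV, also fits the administration times in protocol 1.4: 4 to 7 hours for IV against 3 to 5 minutes for SC.

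**The case against.** The best defence is that little is lost. Interruptions are counted in SAP 4.7. IRRs are reported in detail in 6.3.1, and their rate comes first in the secondary testing order. Fatal TEAEs (6.1.8), deaths (6.2) and second primary malignancies (6.3.6) have their own summaries. Protocol 6.5 and SAP 2.3 name dose delay (the SAP adds dose skip) as the primary way of managing drug toxicity, so the 6.1.7 list follows the documents' own idea of a modification. All of this stands, and it reduces the 6.1.7 gap to one missing cross-tabulation.

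The defence also notes that the eCRF page is not in the documents, that SAP 4.1 speaks of reasons in the plural, and that the grounds in protocol 10.1 are not shown to be eCRF options. A toxicity hold may well be entered as an adverse event. That is fair: a single recorded reason is a sound inference from protocol 10.1, not a demonstrated fact. It limits how firmly the omission can be asserted but does not remove it.

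Three stronger readings are tempting and are not supported:
- *That the rules depend on site or route.* Both are worded the same for every site and both arms. Staff do choose the reason knowing the route, because the trial is open-label, but no passage shows that this varies.
- *That pausing for an IRR is the protocol's main response to adverse events.* It is the prescribed response to IRRs. Dose delay is the stated primary method for toxicity.
- *That the undercount can be read from earlier studies.* Adding the 3 deaths to the 6 discontinuations to get 9 of 156 assumes that the two groups do not overlap and that every death is filed under another reason. The protocol says neither. Reading 120 IV subjects (50% of 240) and 58 SC subjects (24% of 240) as interrupted assumes every IRR occurred during dosing. Protocol 1.3.2 places the Dara-MD reactions during or up to 6 hours after the start of the first administration, and Dara-MD volumes reached 90 mL against 15 mL here.

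Finally, leaving out interruptions that fall mainly on IV would not flatter the SC product.

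**Conclusion.** The point holds in limited form. The 6.1.6 table can omit TEAEs that led to withdrawal when another primary reason is filed. The 6.1.7 table leaves interrupted or stopped administrations out of the adverse event tables by SOC and PT, although 4.7 reports them as exposure data. The second omission would probably weigh more on the IV arm, given the earlier IRR rates and the length of infusion. The size of either effect cannot be computed, and the ranges above show only how far it depends on unknown shares.

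The conclusion on 6.1.6 rests on the End of Treatment page holding one primary reason. Severity is minor: the matter concerns safety reporting only and does not affect either co-primary test, the IRR-rate test, alpha or sample size.

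**What to change.** - **SAP 6.1.6:** count a TEAE if its event-level action taken is permanent withdrawal of study drug, or if the subject's End of Treatment reason is an adverse event. Add a footnote reconciling the count to the disposition table, and state that the overview line in 6.1.1 uses the same definition.
- **SAP 6.1.7:** where the eCRF links the action to the event, add columns for administration interrupted, rate decreased and stopped early. Keep them apart from delays and skips, and cross-refer to 4.7.

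The cost is SAP wording and programming. The SAP indicates that action taken and actions during administration are collected, but the eCRF should be checked for a withdrawal code and for the link between event and action. The downside is that the adverse event and disposition tables may differ by a few subjects, which the footnote would explain.

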### **6.1.7. TEAEs Leading to Treatment Modifications**

Incidence of TEAEs leading to treatment modifications (i.e., cycle delay, dose delays, or dose skip) will be summarized by SOC, PT and grade 3/4 for each treatment group.

### **6.1.8. TEAEs with Fatal Outcome**

The TEAEs with fatal outcome will be summarized by PT and relationship to study drug for each treatment group. A listing of TEAEs with fatal outcome will also be provided.

## **6.2. Deaths**

The number of subjects who died during the study and the primary causes of death will be summarized for the ITT analysis set. In addition, the similar summaries will be presented for all deaths within 30 days of last dose and deaths within 60 days of first dose, respectively.

A listing of subjects who died during the study will be provided.

## **6.3. Adverse Events of Clinical Interest**

### **6.3.1. Infusion-related Reactions**

#### **6.3.1.1. Rate of Infusion-related Reactions**

For the major secondary endpoint of rate of IRRs, the proportion of subjects who have an IRR along with its 95% Clopper-Pearson exact CI will be calculated for each treatment group on the safety analysis set.

Stratified CMH test will be used to test the IRR rate. The CMH estimate of odds ratio and its 2-sided 95% confidence interval and p-value will be reported. Stratification factors used in the analysis include body weight at baseline ( $\leq 65$  kg, 66 kg to 85 kg,  $>85$  kg), number of prior lines of therapy ( $\leq 4$  prior lines versus  $>4$  prior lines), and type of myeloma (IgG versus non-IgG).

A subgroup analysis on rate of IRRs will be conducted for the subgroups of race and baseline weight defined in Section 2.10. A forest plot of the subgroup analysis on rate of IRRs will be generated.

#### **6.3.1.2. Summary of Infusion-related Reactions**

The incidence of infusion-related reactions (IRRs), as recorded on eCRF, will be presented by SOC, PT, and toxicity grade 3/4. In addition, the total number of subjects with IRR in more than

1 infusion will be presented. Time to onset of IRR will be summarized descriptively. The timing of IRR will also be evaluated through a summary of IRR by event onset time.

A listing of infusion-related reactions will be provided.

### **6.3.2. Injection-site Reactions**

For the Dara SC treatment group, injection-site reactions will be recorded on eCRF. The incidence of injection-site reactions will be summarized by SOC, PT, and toxicity grade 3/4. A listing of injection-site reactions will be provided.

### **6.3.3. Infections and Infestations**

Infections and infestations refer to the adverse events with SOC of infections and infestations. The grade 3 or 4 treatment-emergent infections and infestations will be summarized by preferred term and relationship to treatment. Treatment-emergent infections and infestations may also be summarized by preferred term and treatment cycles.

### **6.3.4. Hemorrhage Events**

Hemorrhage events refer to the adverse events defined by Standardized MedDRA Queries (SMQ) with the first subcategory SMQ of hemorrhage terms (exclude laboratory terms). Incidences will be summarized by MedDRA system organ class and preferred term. The summaries will be presented by all grades and maximum toxicity grade for each treatment group.

### **6.3.5. Tumor Lysis Syndrome**

Tumor lysis syndrome (TLS) events refer to the adverse events defined by narrow SMQ of tumor lysis syndrome (e.g., haemorrhagic tumour necrosis, tumour lysis syndrome, or tumour necrosis). A listing of subjects who reported any treatment-emergent TLSs during the study will be provided.

